11.2. Statistical Methodology

11.2.1. Analysis sets

All quantitative analyses will be conducted using the intention-to-treat analysis set.

11.2.2. Null and Alternative Hypothesis

The null hypothesis is that there will be no differences between the active treatment and waitlist control groups on any of the primary or secondary endpoints of the study, while the alternative hypothesis is that there will be differences between the participant groups on these endpoints.

11.2.3. Efficacy Analyses

The analytic plan matches the Australian FMW RCT exactly (Beatty et al., 2019). Data analyses are powered to undertake Mixed Model Repeated Measures analyses to examine intervention effects on change from baseline to follow-up for each outcome (intention-to-treat analysis). Two models will be run for each outcome: (i) unadjusted, accounting for co-variance of baseline measures of outcomes; and (ii) fully adjusted, controlling for all potential confounding variables assessed. Sensitivity analyses will evaluate the effects of missing data. Cohen's *d* effect sizes reflect intervention effects, and clinically significant changes will be assessed using Reliable Change Indices.

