8.8.3. DASS-21

The Depression, Anxiety, and Stress Scales, 21-item version (DASS-21) (Lovibond & Lovibond, 1996) is a short measure of negative emotions experienced over the course of the past week for the individual. Each item is presented as a 4-point Likert scale, anchored as 0 ("Did not apply to me at all"), 1 ("Applied to me some degree, or some of the time"), 2 ("Applied to me to a considerable degree or a good part of the time"), and 3 ("Applied to me very much or most of the time"). The total score for each subscale of the 21-item DASS-21 is calculated by summing participants' responses to the items for each subscale and multiplying this sum by two. Higher scores for each subscale therefore indicate greater levels of depression, anxiety, and stress, respectively. The depression scale of the DASS-21 is associated with excellent internal consistency reliability (α = .91) (Lovibond & Lovibond, 1995). The anxiety scale and the stress scale of the DASS-21 are both associated with good internal consistency reliability (α = .81 and α = .89, respectively) (Lovibond & Lovibond, 1995). The DASS-21 has good concurrent validity, including strong, positive correlations with other measures of depressive symptoms and anxiety (P. F. Lovibond & Lovibond, 1995).

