8.8.5. The PIC

The PIC (Hulbert-Williams et al., 2019) is a 12-item self-report measure of psychological adjustment to cancer. Each item is presented on a 4-point Likert scale anchored from "Definitely does not apply" to "Definitely does apply". The PIC yields four subscale scores: Cognitive Distress, Cognitive Avoidance, Emotional Distress, and Fighting Spirit. For the purposes of the current study, we will only analyse the Cognitive Distress, Cognitive Avoidance, and Emotional Distress subscales. All subscales are associated with at least fair internal consistency reliability ($\alpha > .623$) and good concurrent validity with longer measures of psychological adjustment to cancer (Hulbert-Williams et al., 2019).

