11. STATISTICAL AND DATA ANALYSIS

11.1. Sample Size Calculation

Calculations are based on the primary outcome of change in cancer distress between the two patient groups. The original FMW randomised clinical trial sample size calculation used a standardised effect size of 0.35 and standard deviation of 4 units, which equates to an absolute change in cancer distress scores of 1.4 units. This study observed a larger than expected standard deviation and we propose a sample size based on a conservative estimate of the residual standard deviation of 7 units accordingly (but keeping the clinically relevant difference at the aforementioned 1.4 units). Correlation between successive measurements on the same patient are assumed to be high and a conservative r=0.7 is used. Sample size calculations are performed assuming a paired t-test using a derived standard deviation about the change in the primary outcome of 5.42. Assuming a patient attrition of 20% and a two-sided alpha=0.05, then 294 patients (147 per study arm) are required for statistical power of 80%.

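### Section 11.2.3 says the analyses are powered for each outcome, but the only sample size calculation concerns the primary distress scale, so the claim has no support for any secondary outcome

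*Protocol*

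**What the plan says.** Protocol section 11.2.3 (Efficacy Analyses) says: "Data analyses are powered to undertake Mixed Model Repeated Measures analyses to examine intervention effects on change from baseline to follow-up for each outcome".

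Section 11.1 (Sample Size Calculation) opens: "Calculations are based on the primary outcome of change in cancer distress between the two patient groups". Its inputs all belong to that scale: "keeping the clinically relevant difference at the aforementioned 1.4 units", a "conservative estimate of the residual standard deviation of 7 units", and for the correlation, "a conservative r=0.7 is used". The calculation is done "assuming a paired t-test using a derived standard deviation about the change in the primary outcome of 5.42". With 20% attrition and two-sided alpha 0.05, it arrives at 147 per arm (294 in total) for 80% power.

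Section 4.4 lists the secondary endpoints: DASS-21, QLQ-C30, PIC and the UK Cancer Costs Questionnaire. Section 8.8 describes these instruments. For the DASS-21, QLQ-C30 and PIC it gives internal-consistency figures, but it gives no anticipated effect, SD or between-visit correlation for any of them.

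**The concern.** As written, the sentence in 11.2.3 attaches adequate power to every outcome. Two neighbouring sections strengthen that reading: 11.2.2 states one null hypothesis spanning primary and secondary endpoints, and 11.3 applies p < 0.05 without distinguishing them. Yet 11.1 supports a power statement for one scale only. A difference of 1.4 units with SD 7 on the distress scale says nothing about a DASS-21, QLQ-C30 or PIC subscale.

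Four secondary objectives in 4.2 depend on these outcomes: anxiety, depression and stress; quality of life; adjustment; and service use. The Background reports that the earlier Australian trial found its benefits in emotional functioning and service use, not in distress, so secondary results may well carry weight here. A reader told that each outcome was powered could take a non-significant secondary result as evidence of no benefit, and nothing in the design supports that inference.

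**Working it through.** **1. Reproduce section 11.1.** Inputs: difference 1.4, SD 7, r = 0.7, attrition 20%, two-sided alpha 0.05, power 80%.

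- SD of change = 7 × √(2 × (1 − 0.7)) = 5.42.
- Paired (one-sample) formula: n = ((1.960 + 0.842) × 5.42 / 1.4)² = 117.6.
- Attrition: 117.6 / 0.80 = 147.05, taken as 147 per arm, 294 in total.

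The printed figure reproduces, but only with the one-sample paired formula applied within each arm.

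**2. Look for the same inputs on the secondary outcomes.**

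| Input | Primary scale | Any secondary outcome |
|---|---|---|
| Target difference | 1.4 units | not given |
| SD | 7 | not given |
| Correlation | 0.7 | not given |
| Power | 80% | not given |

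No calculation for a secondary outcome can be rebuilt from the protocol. For service use, section 11.2.4 plans descriptive summaries and generalised linear models, so a claim of power for mixed-model analyses fits it even less well.

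**3. Detectable difference that needs no input for a particular scale.** Completers per arm: 147 × 0.80 = 117.6, about 118. For a two-arm comparison of change at a single time point:

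- Detectable at 80% power = (1.960 + 0.842) × √(2/118) = 0.365, about 0.37 SD of change.
- Primary target on the same scale = 1.4 / 5.42 = 0.258, about 0.26 SD of change.
- Power at that target = Φ(0.258 × √(118/2) − 1.960) = 51%.
- With baseline as covariate: SD = 7 × √(1 − 0.49) = 5.00, and power = Φ((1.4/5.00) × √(118/2) − 1.960) = 58%.
- For 80% power on the two-arm change comparison: 236 completers per arm, 236 / 0.80 = 295 randomised per arm, 590 in total.

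**4. What the reliability figures can and cannot show.** Section 8.8 gives alpha .91 for the primary scale and .91 for DASS depression, .89 for DASS stress, .86 for QLQ-C30 global, .81 for DASS anxiety and above .623 for the PIC subscales. *Assume* the true standardised effect equals that of the primary scale. For reliability a, multiply the observed effect by √(a/.91). Keep the paired method and 117.6 completers. Then either hold r at 0.7 or also reduce it to 0.7 × a/.91:

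| Scale | r held at 0.7 | r reduced too |
|---|---|---|
| DASS depression (.91) | 80% | 80% |
| DASS stress (.89) | 79% | 77% |
| QLQ-C30 global (.86) | 78% | 73% |
| DASS anxiety (.81) | 75% | 65% |
| PIC at the .623 bound | 64% | 42% |

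With r held at 0.7, a true effect on the PIC larger by √(.91/.623) = 1.21, or 21%, would cancel the loss entirely.

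**The case against.** The strongest reply is that the phrase about each outcome describes the scope of the analyses and not the power, and that 11.1 openly says the calculation rests on the primary outcome. Sizing on the primary alone is ordinary practice. The protocol nowhere says that p > 0.05 will be read as no effect, and it already plans Cohen's d (11.2.3) and 95% intervals (11.3). All of this limits the seriousness of the point. It does not remove it: the grammar makes the analyses for each outcome the thing that is powered, and no other text supplies the missing calculations.

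A reader might go further and infer that the protocol's own reliability figures prove power well below 80% on the secondary scales. They do not:

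- The table in step 4 needs an equal true effect on every scale, which the protocol does not state. The earlier trial's results, as reported in the Background, differed by outcome.
- Internal consistency is not the correlation between visits, so the right-hand column uses a stand-in.
- The PIC statement, "All subscales are associated with at least fair internal consistency reliability", covers four subscales with a lower bound, and section 8.8.5 says only three are analysed. The lowest value may belong to the one left out.
- DASS depression loses nothing, and with r held at 0.7 only the PIC bound falls far below 80%.

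A reader might equally take 80% as a sound figure for the primary outcome. On a two-arm comparison at a single time point it is not. The 51–58% does depend on which contrast is tested. If the effect were constant and the test averaged all four post-baseline assessments, with baseline adjustment and every pairwise correlation equal to 0.7, the SD would be 7 × √((1 + 3 × 0.7)/4 − 0.49) = 3.74 and power about 82% with 118 completers per arm. The protocol does not say that this average is the primary test.

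**Conclusion.** The claim of power for each outcome is unsupported and should not stand. This conclusion needs no assumption: it follows from setting 11.2.3 beside 11.1. It is a wording fault with consequences for interpretation, not evidence that the secondary analyses are underpowered by a known amount. The values for anxiety (65–75%) and PIC (42–64% at the bound) illustrate what could happen if the true standardised effect matched that of the primary scale, and should be presented only as that.

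The 0.37 SD figure rests on 118 completers per arm, a two-arm comparison of change and a single time point. It applies to the primary outcome as much as to the others, so it cannot be printed for secondary outcomes beside an unchanged claim of 80% power at 0.26 SD for the primary with the same completers.

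**What to change.** In 11.2.3, remove the statement that the analyses are powered for each outcome and put in its place, for example:

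> The sample size was set on the primary outcome only. No power is claimed for secondary outcomes. These are interpreted from effect estimates with 95% confidence intervals, and p > 0.05 is not read as absence of effect.

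If a detectable difference is printed, give it once and on one basis for all outcomes: about 0.37 SD of change at 80% power, with about 118 completers per arm, for a two-arm comparison of change at a single time point. In that case correct the power statement in 11.1 on the same basis, so that it gives about 51% for the 0.26 SD target, or define the between-arm contrast on which the sizing does rest and give its assumptions. Omit reliability-based power values, or label them as illustrations with the equal-effect assumption stated.

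The change to 11.2.3 costs only wording and needs no additional patients. The correction to 11.1 makes the stated power less favourable. Keeping 80% for a single-time-point comparison of change would take about 590 patients instead of 294.

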11.2.4. Health Economic Analyses

The healthcare utilisation outcome will be summarised descriptively for activity counts and cumulative costs. Generalised linear models will be used to adjust for the same confounding variables as the efficacy analysis.

11.3. Significance and Confidence Level

p-values < 0.05 will be considered significant. All confidence intervals will be at the 95% level.

11.4. Qualitative Data Analyses

Qualitative interviews will be analysed using thematic analysis (Braun & Clarke, 2006).

11.5. Criteria for Terminating the Study

No interim analysis is planned. The study will be terminated prematurely only on the grounds of exceptional, unforeseen safety concerns or exceptional, unforeseen recruitment issues.

11.6. Procedure for Accounting for Missing, Unused or Spurious Data

We will conduct data cleaning to ensure that all data values are possible and plausible. Errant data entries will be deleted from the final analysis data set and missing data will be handled as specified for the psychometric measure from which there is a missing response.

11.7. Procedure for Reporting Deviations from the Statistical Plan

In the event that a deviation from the statistical analysis plan becomes necessary or desirable, the reasons for doing so will be set out in the clinical study report.

Version 5.0 Page 37 of 45 IRAS No. 288469

12. DATA HANDLING

12.1. Data Collection Tools and Source Document Identification

12.1.1. Clinical data collection

Clinical Research Network staff will screen participants' medical records for the clinical data described in Section 8.7.8. Clinical Research Network staff will send these data to the research team securely via an encrypted email or encrypted email attachment.

12.1.2. The web based data collection system

We will collect study data for the online surveys using Qualtrics. Qualtrics is a secure online survey system. The research team will be able to export all study data into an encrypted master database and a separate encrypted contact details database.

12.2. Data handling and Record Keeping

The Sponsor will ensure that all data is processed in accordance with UK Data Protection Law. Once all data have been entered, verified, and validated in the master database, the database will be locked.

12.3. Access to Data

Direct access to source data will be granted to authorised representatives from the Sponsor, auditors, the REC, and the regulatory authorities to permit trial-related monitoring, audits and inspections.

12.4. Archiving

The research team agrees to retain a copy of the protocol, documentation, approvals and all other documents related to the study, including data, for 10 years after the end of the study.

13. ADMINISTRATIVE MATTERS

13.1. Responsibilities of the Investigator

- To ensure that he/she has sufficient time to conduct and complete the study, and has adequate staff and appropriate facilities which are available for the duration of the study and to ensure that other studies do not divert essential subjects or facilities away from the study at hand.
- To submit an up-to-date curriculum vitae for themselves and sub-investigators, and other credentials to the sponsor and, where required, to REC and relevant competent authorities.
- Demonstrate a potential for recruiting the required number of suitable subjects within the agreed recruitment period.
- Conduct the study in accordance with the relevant, current protocol and only make changes after notifying the sponsor, except when protect of the safety, rights, or welfare of the subjects is paramount.

- Record any deviations from the protocol.
- Comply with guidance on Good Clinical Practice.
- Personally conduct or supervise the described investigation.
- Ensure that the requirements relating to obtaining informed consent and ethics review and approval have been met.
- Follow the trial's randomisation procedure and ensure the treatment code is broken only in accordance with the protocol.
- Maintain adequate and accurate records and make these available for inspection by the sponsor [and/or its designee] or any agency authorised by law.
- Ensure that a REC, compliant with local regulations, will be responsible for the initial and continuing review and approval of the clinical investigation.
- Promptly report to the REC all changes in the research activity and all unanticipated problems involving risks to human subjects or others.
- Comply with all other requirements regarding the obligations of clinical investigators and all other pertinent requirements'
- Ensure that all associates, colleagues, and employees assisting in the conduct of the study are appropriately qualified and informed about their obligations in meeting the above commitments.
- Maintain a list of appropriately qualified persons to whom the investigator has delegated significant trial-related duties.
- Inform the sponsor of any changes to staff or facilities.

13.2. Monitoring by Sponsor or Their Representative

The research team will provide the sponsor with copies of the annual reports submitted to the relevant ethical approval bodies.

14. ETHICAL AND REGULATORY CONSIDERATIONS

This study will be conducted according to Good Clinical Practice guidelines, local regulatory requirements and the 2013 Declaration of Helsinki.

14.1. Ethics Approval

This protocol will be submitted to the appropriate REC and their written, unconditional approval obtained and submitted to the sponsor before commencement of the study.

Verification of the ethics committee's unconditional approval of the protocol, participant information sheet and informed consent document will be transmitted to Sponsor prior to the commencement of the study.

The written, unconditional approval from the ethics committee must refer to the study by exact protocol title and number, identify the documents reviewed and state the date of review. Any amendment to the protocol must be approved in the same way.

The ethics committee must be informed by the investigators of all subsequent protocol amendments and of serious or unexpected adverse experiences occurring during the study which are likely to affect the safety of the subjects or the conduct of the study. Approval for such changes must be transmitted in writing to Sponsor via the investigators.

All correspondence with the REC will be retained in the study documentation.

14.2. Peer Review

The initial grant application for this clinical trial underwent a peer review process consisting of independent, external patient and expert reviewers recruited by North West Cancer Research, who approved the study's design. A Trial Steering Group consisting of oncologists, health economists, and psychologists from multiple academic institutions in the UK and Australia, as well as patient, caregiver, and healthcare professional representatives, maintain oversight of the clinical trial on an ongoing basis. The study has also been reviewed by the Ethics Committee for the Department of Psychology at the University of Chester.

14.3. Protocol Compliance

Prospective, planned deviations or waivers to the protocol are not allowed under the UK regulations on Clinical Trials and must not be used (e.g., it is not acceptable to enrol a subject if they do not meet the eligibility criteria or restrictions specified in the trial protocol).

Accidental protocol deviations can happen at any time. They must be adequately documented on the relevant forms and reported to the Sponsor.

14.4. Notification of Serious Breaches to GCP and/or the Protocol

A "serious breach" is a breach which is likely to effect to a significant degree:

- (a) the safety or physical or mental integrity of the subjects of the trial; or
- (b) the scientific value of the trial

The sponsor must be notified immediately of any case where the above definition applies during the trial conduct phase.

All protocol breaches will be documented and reported in the final study report.

14.5. Data Protection and Patient Confidentiality

All investigators and trial site staff must comply with the requirements of the Data Protection Act 2018 with regards to the collection, storage, processing and disclosure of personal information and will uphold the Act's core principles.

The Chief Investigator will act as custodian for the research data. All data will be kept completely confidential and will be anonymised and will only be considered in relation to the

project. All audio-recordings made will be suitably anonymised, securely stored in password protected computers and made accessible only to the investigators.

14.6. Financial and Other Competing Interests for the Chief Investigator, Investigators at Each Site and Committee Members for Overall Trial Management

This information will be collected for all participants and retained in the Trial Master File.

14.7. Indemnity

The sponsor will provide Public Liability, Professional Indemnity, and Clinical Trials insurance cover.

14.8. Amendments

Protocol amendments must be made only with the prior approval of Sponsor. Agreement from the Investigator must be obtained for all protocol amendments and amendments to the informed consent document.

The REC must be informed of all amendments and give approval for any amendments.

Any amendment/modification to the protocol will be adhered to by the participating centre (or all participating centres) and will apply to all subjects following its approval.

This will be communicated by the Trial Coordinator and checked for implementation as relevant.

Tracking of the amendment history will be retained in the Trial Master File.

14.9. Post-Trial Care

Participants will be referred to their regular treatment team for any concerns about their physical or mental health following the completion of the randomised controlled trial.

15. DISSEMINATION POLICY

15.1. Dissemination Policy

The clinical trial data will be published in relevant peer-reviewed journals as a joint effort of the trial Steering Group without undue delay following the completion of the study.

